¹ An Unscheduled Relapse Assessment Visit will be conducted within 72 hours of symptom onset of a suspected relapse (i.e., new or recurrent neurologic symptom[s]).

² Discontinuation refers to discontinuation of study treatment. Withdrawal refers to withdrawal of subjects from the study. The Discontinuation/Withdrawal Visit should be conducted as soon as possible and no later than 4 weeks after the last dose of study treatment.

CONFIDENTIAL

The information contained herein may not be used, disclosed, or published without the written consent of Biogen MA Inc.

³ Subjects who complete, temporarily withhold, or permanently discontinue study treatment for any reason and have a lymphocyte count <LLN will continue protocol-required visits and assessments and be followed every 4 weeks for 24 weeks and then every 3 months (**unless clinically indicated more often or at the Investigator's discretion**) until the lymphocyte count is \geq LLN or for 52 weeks after the last dose, or until one of the following occurs: 1) the subject continues on commercial BG00012 following study withdrawal/completion, or 2) the subject is initiated on another MS disease-modifying therapy. Note: lymphocyte counts \geq LLN at 2 consecutive visits are required.

⁴ Vital signs include body temperature, pulse rate, and systolic/diastolic blood pressure measurements.

⁵ Hematology testing must be performed every 4 weeks in subjects with lymphocyte count <LLN.

⁶ Study treatment must be temporarily withheld or permanently discontinued if any of the laboratory values meet the criteria defined in the protocol.

⁷ For females of childbearing potential.

⁸ Urine cytology must be performed if a subject experiences hematuria (of unknown etiology) at 2 consecutive visits or at the Unscheduled Relapse Assessment Visit or the Discontinuation/Withdrawal Visit.

⁹ An MRI must not be performed within 30 days of receiving a course of steroids.

¹⁰ A brain MRI scan will be performed unless assessed in the last 30 days.

CONFIDENTIAL

The information contained herein may not be used, disclosed, or published without the written consent of Biogen MA Inc.

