10. DISCONTINUATION OF STUDY TREATMENT AND/OR WITHDRAWAL OF SUBJECTS FROM THE STUDY

10.1. Discontinuation of Study Treatment

A subject *must* permanently discontinue BG00012 for any of the following reasons:

- The subject becomes pregnant. Study treatment must be discontinued immediately. Report the pregnancy according to the instructions in Section [15.4.1](#).
- The subject experiences a medical emergency that necessitates permanent discontinuation of study treatment.
- The subject has lymphocyte count $<500/\text{mm}^3$ for 6 months as outlined in [Table 4](#) and [Table 5](#).
- The subject experiences a protocol-specified change in laboratory values that necessitates permanent discontinuation of treatment as outlined in [Table 3](#) and [Table 4](#).
- The subject cannot tolerate study treatment.
- The subject receives any of the disallowed concomitant medications for this study.
- The subject or subject's parent/legal guardian desires to discontinue treatment.
- At the discretion of the Investigator for medical reasons or for noncompliance.

The reason for discontinuation of study treatment must be recorded in the subject's eCRF.

Subjects who discontinue treatment may remain in the study and continue protocol-required tests and assessments.

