AE = adverse event; ALT = alanine transaminase; AST = aspartate transaminase; SGOT = serum glutamic oxaloacetic transaminase; SGPT = serum glutamic pyruvic transaminase; ULN = upper limit of normal; WBC = white blood cell.

[Table 4](#) describes the management of lymphocytes <LLN for subjects during and after study treatment.

CONFIDENTIAL

The information contained herein may not be used, disclosed, or published without the written consent of
Biogen MA Inc.

Table 4: Management of Lymphocyte Count <LLN

Laboratory Parameter	Laboratory Result	Required Action
Lymphocyte count on study treatment	<LLN	The Investigator should repeat the test within 2 weeks. If retest confirms that lymphocyte count is <LLN, lymphocyte count should be closely monitored (at least every 4 weeks).
Lymphocyte count on study treatment	<500/mm ³	If lymphocyte count is <500/mm ³ for more than 6 months, study treatment must be permanently discontinued.
Lymphocyte count in subjects who complete, temporarily withhold, or permanently discontinue BG00012 for any reason	<LLN	Subjects will be followed at least every 4 weeks for 24 weeks and then every 3 months (unless clinically indicated more often or at the Investigator's discretion) until the lymphocyte count is \geq LLN ¹ or for 52 weeks after the last dose, or until one of the following occurs: 1) the subject continues on commercial BG00012 following study withdrawal/completion, or 2) the subject is initiated on another MS disease-modifying therapy.

LLN = lower limit of normal; MS = multiple sclerosis.

¹ Lymphocyte counts \geq LLN at 2 consecutive visits are required.

While dosing is withheld, subjects will continue tests and assessments according to [Table 1](#) (and may also undergo additional assessments to evaluate the laboratory abnormality as per the Investigator's standard practice). In addition, subjects (whether on study treatment, having dosing temporarily withheld, or permanently discontinued) must have the abnormal laboratory result rechecked at the central laboratory as follows:

- For all analytes, with the exception of lymphocytes, results will be rechecked at least every 2 weeks until resolution or stabilization of the laboratory value. Depending on the severity and clinical significance of the abnormality, the Investigator may need to perform the retests more frequently.

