11.6. Continuation of Treatment

There is no provision for additional courses of BG00012 provided by Biogen beyond the treatment period defined in this protocol.

If and when BG00012 is commercially available at the time the study treatment period is completed, subjects will be allowed to take commercial BG00012 during the Safety Follow-Up Period if deemed appropriate by product labeling and at the discretion of their treating physician.

CONFIDENTIAL

The information contained herein may not be used, disclosed, or published without the written consent of
Biogen MA Inc.

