### **6.3.2.3 Clinical Laboratory Data**

The following clinical laboratory parameters are assessed per the protocol:

- Hematology: hemoglobin, hematocrit, red blood cell count, WBC count (with differential) and platelet count.
- Blood chemistry: albumin, sodium, potassium, chloride, total bilirubin, alkaline phosphatase, ALT, AST, GGT, blood urea nitrogen, creatinine, bicarbonate, calcium, magnesium, phosphate, uric acid, and glucose
- Vitamin D and PTH (Day 1 and Week 96 only)
- Urine and serum pregnancy tests

Each laboratory value for each subject will be flagged as ‘low’, ‘normal’, or ‘high’, relative to the parameter’s normal range. Each subject’s urinalysis values will be flagged as “positive”, “negative”, or if no value is available, “unknown”.

Shifts from baseline to post baseline (Week 4/early withdrawal) high/low status for all hematology and blood chemistry parameters, and shifts from baseline to high/positive status for urinalysis will be presented.

Summary statistics will also be provided for all absolute laboratory values as well as change from baseline. The summaries for laboratory data will be data from baseline to each time point, including early withdrawal. Graphs showing the mean or change from baseline values may be presented as well.

In addition to lymphocyte count data summarized at each timepoint on study treatment, lymphocyte count over time post-treatment and the time to recovery will be descriptively summarized for subjects who develop decreases in lymphocyte count (<LLN).

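### Laboratory summaries ignore dosing status: off-drug values can enter the by-visit and shift tables, and a count taken on commercial BG00012 can be labelled post-treatment

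*SAP*

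**What the plan says.** **Summaries.** SAP 6.3.2.3 gives absolute values and changes from baseline by time point: "The summaries for laboratory data will be data from baseline to each time point, including early withdrawal". The shift tables are described as "Shifts from baseline to post baseline (Week 4/early withdrawal) high/low status for all hematology and blood chemistry parameters", with a matching shift for urinalysis. Neither rule mentions the last dose or drug status. Lymphocytes alone get a divided treatment: "In addition to lymphocyte count data summarized at each timepoint on study treatment, lymphocyte count over time post-treatment", the latter together with time to recovery, for subjects who fall below the lower limit of normal (LLN).

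**Testing off drug.** Protocol 11.2.1 says "While dosing is withheld, subjects will continue tests and assessments according to" Table 1. Protocol 10.1 adds: "Subjects who discontinue treatment may remain in the study and continue protocol-required tests and assessments". The Discontinuation/Withdrawal Visit "should be conducted as soon as possible and no later than 4 weeks after the last dose of study treatment" (Protocol 4.2, Table 2, footnote 2). SAP 6.1.7 can then assign that visit's data to the next scheduled visit if it falls within the ±5-day window.

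**Commercial drug.** After the treatment period, subject to availability, labelling and the treating physician's judgement, "subjects will be allowed to take commercial BG00012 during the Safety Follow-Up Period" (Protocol 11.6). Table 1 schedules hematology at the Safety Follow-Up Visit.

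**Baseline.** Inclusion criterion 2 requires ongoing BG00012 240 mg BID, and SAP 6.1.1 takes baseline from the end of the parent study or Day 1. Baseline is therefore an on-drug value.

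**The concern.** Long-term safety is the primary objective, and a reader will take the by-visit laboratory tables as describing subjects on BG00012. Protocol Table 3 requires dosing to be withheld because a transaminase, creatinine, WBC or urinalysis result is confirmed abnormal. Samples taken during withholding therefore come selectively from subjects who showed a laboratory signal, at a time when some may be recovering. Mixed without a marker into tables of change from an on-drug baseline, they make the table answer a different question from the one the reader has in mind.

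The lymphocyte recovery summary has the reverse problem. Its purpose is to show what happens once BG00012 stops, but nothing in the SAP removes a subject who has resumed the same drug commercially or moved to another MS therapy.

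**Working it through.** The plan states no figure to reproduce. The check sets the passages side by side and then adds simple mixture arithmetic.

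**1. Where unflagged samples can land**

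| Sample | Source | Place in the SAP tables |
|---|---|---|
| Scheduled test while dosing is withheld | Protocol 11.2.1 | By-visit values and changes (6.3.2.3) |
| Scheduled test after permanent stop | Protocol 10.1 | Same |
| Recheck while withheld (non-lymphocyte analytes, at least every 2 weeks) | Protocol 11.2.1 | By-visit row, if it is the value nearest the target day (6.1.7) |
| Withdrawal sample, up to 4 × 7 = 28 days after last dose | Protocol Table 2 | Early-withdrawal row and shift table, or a scheduled visit (6.1.7) |
| Safety Follow-Up count on commercial BG00012 | Protocol 11.6, Table 1 | Post-treatment lymphocytes, if below LLN |

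**2. Shift table.** Its named post-baseline points are Week 4 and early withdrawal. The schedule has no Week 4 visit; the first post-baseline visit is Week 12. Read literally, the only named point that exists is one that may be off drug. Protocol 16.5.1.2 speaks only of the incidence of shifts outside the normal range and does not say which post-baseline value counts.

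**3. Direction and size of the by-visit effect (illustration).** Protocol 5.3.2 reports that mean WBC in adults fell about 10% in the first year and then plateaued. Set the untreated level to 100, so on-drug baseline is 90 and the true on-drug change is 0. If a share f of samples is off drug and fully recovered:

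observed mean = 90(1 − f) + 100f = 90 + 10f; apparent change = 10f/90.

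| f (assumed) | Apparent change from on-drug baseline | Reading if baseline were untreated, −10%(1 − f) |
|---|---|---|
| 5% | +0.6% | −9.5% |
| 10% | +1.1% | −9% |
| 20% | +2.2% | −8% |
| 30% | +3.3% | −7% |

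The middle column applies here: a false rise, not a shrunken fall.

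**4. Post-treatment lymphocytes (illustration).** Take the adult fall of about 30%. If a share g of the subjects below LLN are on commercial BG00012 at the Safety Follow-Up Visit and the rest have fully recovered, the mean deficit reads −30% × g instead of 0. For g = 10%, 25%, 50%, 75% this gives −3%, −7.5%, −15%, −22.5%. Full recovery by 4 weeks is a bounding assumption, and subjects below LLN may differ from the adult mean.

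**5. How far this reaches.** The follow-up schedule allows about 24/4 = 6 visits and then 28/13 ≈ 2 more. Protocol version 3.0 (7.2.3, Table 4) ends this follow-up when the subject continues on commercial BG00012 or starts another MS therapy. Under that text only the Safety Follow-Up sample, about one in eight, should be drawn on commercial drug. After that the issue is follow-up that ends without recovery, for which the SAP gives no censoring rule. SAP Section 3, Table 2, footnote 3 ends follow-up only on recovery or at 52 weeks, so it does not match the current protocol.

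**The case against.** The case against is substantial. The study is single-arm and descriptive, and the primary endpoint is adverse events and treatment discontinuations, not laboratory means. Table 3 abnormalities that lead to permanent stopping must be recorded as adverse events, and the SAP tabulates and lists discontinuations due to adverse events separately. An abnormal value that triggers withholding was drawn on drug and stays in its own visit row. Most rechecks miss the visit windows: with eight on-treatment hematology visits in version 3.0, the windows cover 8 × 11 = 88 of 96 × 7 + 5 = 677 days, about 13%. Restricting tables to on-drug samples also selects subjects who tolerate treatment. Finally, the lymphocyte wording may mean only treatment-period visits, not a sample-level rule.

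All of this limits the consequence, but none of it supplies a drug-status rule. The visits of withheld subjects fall in the windows by design. The selection point is a reason to show both tables.

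Three stronger readings are tempting, and the documents do not support them:

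- **That both sets of results are in fact diluted and a drug effect is hidden.** There are no counts, and an on-drug baseline points to a spurious change instead.
- **That commercial use contaminates the whole post-treatment lymphocyte series in proportion to the completers who switch.** The summary covers only subjects below LLN, version 3.0 ends their follow-up at that point, and commercial access is conditional.
- **That a subject stopped for ALT or creatinine appears in the shift table only through a recovered sample.** The Week 4 wording leaves the rule undefined. If any post-baseline shift counts, a later normal value erases nothing. Stopping under Table 3 for persistence also requires the value to remain abnormal at least 4 weeks off drug, although the recurrence rule in 11.2.3 and investigator discretion are other routes.

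**Conclusion.** The gap is real and should be closed. As written, off-drug values can enter the by-visit and shift summaries of analytes other than lymphocytes, and because baseline is on drug they can produce a spurious change from baseline. For subjects below LLN, a Safety Follow-Up count taken on commercial BG00012 would be counted as post-treatment, and time to recovery is not censored when commercial BG00012 or another MS therapy starts.

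The size cannot be determined. The documents give no sample size, no rate of withholding or stopping, and no rate of commercial use. The illustrative WBC rise of 0.6% to 3.3% rests on assumed off-drug shares of 5% to 30%, full recovery off drug and an adult effect. The lymphocyte figures rest on similar assumptions and concern one sample per affected subject. The primary endpoint tables are not affected.

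**What to change.** In SAP 6.3.2.3:

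1. Derive one flag per laboratory sample from dosing and concomitant-therapy dates: on study BG00012 (with a lag after the last dose set by the sponsor, and a stated rule for withheld periods), off drug, or on commercial BG00012 or another MS therapy.
2. Base by-visit and shift tables for all analytes on on-drug samples. Tabulate off-drug samples separately so that no value is lost.
3. Exclude samples taken on commercial BG00012 or another MS therapy from the post-treatment lymphocyte summary, and censor time to recovery at those start dates.
4. Reconcile SAP Section 3, Table 2, footnote 3 with protocol version 3.0.
5. Replace the Week 4 time point in the shift table with one that is in the schedule, and state which post-baseline value defines a shift.

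The cost is SAP wording and one derived variable. Dosing data and concomitant therapy are already collected. One check is needed: Protocol 11.5.1 closes the concomitant-therapy period at the Safety Follow-Up Visit, so confirm that therapy start dates during later lymphocyte visits are captured. The downside is slightly fewer values in each on-drug table. Those tables describe subjects still on treatment and should be read alongside the off-drug table.

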7.2.3. Follow-Up

Subjects are to return to the study site for a follow-up visit 4 weeks after their last treatment visit (Visit 10 at Week 96 [± 5 days]).

Subjects who withdraw prematurely from the study will complete the Early Withdrawal Visit, which should be conducted as soon as possible and no later than 4 weeks after the subject's last dose of study treatment. Subjects who withdraw prematurely should be encouraged to complete the Safety Follow-Up Visit 4 weeks after the last dose of study treatment.

Subjects who complete, temporarily withhold, or permanently discontinue study treatment for any reason and have a lymphocyte count less than the lower limit of normal (LLN) will be followed every 4 weeks for 24 weeks and then every 3 months (**unless clinically indicated more often or at the Investigator's discretion**) until the lymphocyte count is \geq LLN or for 52 weeks after the last dose, or until one of the following occurs: 1) the subject continues on commercial BG00012 following study withdrawal/completion, or 2) the subject is initiated on another MS disease-modifying therapy.

CONFIDENTIAL

The information contained herein may not be used, disclosed, or published without the written consent of
Biogen MA Inc.

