**Table 2: Additional Study Activities for Study 109MS311**

Tests and Assessments	Unscheduled Relapse Assessment Visit  (within 72 hours after symptom onset)	Discontinuation/ Withdrawal Visit  (as soon as possible but no later than 4 weeks after last dose of study treatment)	Lymphocyte Follow-Up Visit 
Physical Examination	X	X	X
Body Weight	X	X	X
Height		X	
Vital Signs 	X	X	X
12-Lead ECG		X	
Hematology 	X	X	X
Blood Chemistry 	X	X	
Urine Pregnancy Test 	X	X	
Urinalysis 	X	X	
PTH and Vitamin D Levels		X	
EDSS	X	X	
Brain MRI Scan 		X 	
Relapse Assessment	X		
Concomitant Therapy and Procedures		Monitor and record throughout the study	
AE/SAE Recording		Monitor and record throughout the study	

AE = adverse event; ECG = electrocardiogram; EDSS = Expanded Disability Status Scale; LLN = lower limit of normal; MRI = magnetic resonance imaging; PTH = parathyroid hormone; SAE = serious adverse event.

 An Unscheduled Relapse Assessment Visit will be conducted within 72 hours of symptom onset of a suspected relapse (i.e., new or recurrent neurologic symptom[s]).

 Discontinuation refers to discontinuation of study treatment. Withdrawal refers to withdrawal of subjects from the study. The Discontinuation/Withdrawal Visit should be conducted as soon as possible and no later than 4 weeks after the last dose of study treatment.

 Subjects who complete, temporarily withhold, or permanently discontinue study treatment for any reason and have a lymphocyte count <LLN will continue protocol-required visits and assessments and be followed every 4 weeks for 24 weeks and then every 3 months (unless clinically indicated more often or at the Investigator's discretion) until the lymphocyte count is  $\geq$ LLN or for 52 weeks after the last dose (whichever is sooner).

 Vital signs include body temperature, pulse rate, and systolic/diastolic blood pressure measurements.

 Hematology testing must be performed every 4 weeks in subjects with lymphocyte count <LLN

 Study treatment must be temporarily withheld or permanently discontinued if any of the laboratory values meet the criteria defined in the protocol.

 For females of childbearing potential.

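### Post-treatment lymphocyte counts are averaged over subjects still in follow-up, who are disproportionately slow recoverers, so the by-time summary understates recovery at later time points

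*SAP*

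**What the plan says.** SAP 6.3.2.3 (Clinical Laboratory Data) states that "lymphocyte count over time post-treatment and the time to recovery will be descriptively summarized for subjects who develop decreases in lymphocyte count" to below LLN. Protocol 16.5.1.2 plans the same. SAP Section 6 gives the general statistics for continuous data: number with data, mean, standard deviation, median and range.

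Who is sampled after the last dose is set elsewhere:

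- Protocol 11.2.1, Table 4: "Subjects will be followed at least every 4 weeks for 24 weeks and then every 3 months".
- Protocol 7.2.3: follow-up runs until the count is back at or above LLN, to a maximum of 52 weeks from the last dose. It ends sooner if "the subject continues on commercial BG00012 following study withdrawal/completion", and likewise when another MS disease-modifying therapy is started.
- Protocol 4.2, Table 2 note 3, and the note to Table 4, add that counts at or above "LLN at 2 consecutive visits are required". Sections 7.2.3 and 11.2.5 do not repeat this.
- SAP Section 3, Table 2 (Additional Study Activities), footnote 3: follow-up ends at a count at or above "LLN or for 52 weeks after the last dose (whichever is sooner". It mentions neither the two-visit condition nor the therapy exits.
- Protocol 10.1 and 11.2.5.2: subjects who stop treatment early and stay in the study keep their scheduled tests. For completers, the last scheduled hematology in Table 1 is the Safety Follow-Up Visit, four weeks after the last dose.

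The SAP has no rule for subjects who leave follow-up because they recovered, and no definition of recovery or censoring for the time-to-recovery summary.

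**The concern.** Observation stops because of the variable being summarised. Beyond four weeks after the last dose, a completer contributes a count only while recovery has not been confirmed. A mean or median at Week 24 or Week 50 therefore describes the subjects left in follow-up, not everyone who finished treatment with a low count.

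The time-to-recovery half of the sentence does not repair this as it stands. Mean, median and range have no place for a subject who has not recovered by the end of follow-up. If only recovered subjects contribute, the slowest are left out and recovery looks faster than it was. The two summaries in one sentence could then err in opposite directions.

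Reversibility is a safety question the protocol itself raises: Section 5.3.2 reports progressive multifocal leukoencephalopathy in severe and prolonged lymphopenia.

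**Working it through.** The plan states no recovery rate, number of subjects or expected count for this summary, so there is no figure to reproduce. The check is a simulation of the follow-up rule, with 200,000 subjects per scenario.

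**From the documents.** Four-weekly visits to Week 24 after the last dose, then three-monthly to 52 weeks, coded as Weeks 0, 4, 8, 12, 16, 20, 24, 37 and 50. Two stopping rules: two consecutive counts at or above LLN (protocol v3.0 notes) and one such count (SAP footnote 3).

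**Assumed, in multiples of LLN.**
- Starting count C0 uniform on 0.40 to 0.95.
- Plateau P log-normal (log-SD 0.2), not below C0.
- Recovery half-time h log-normal (log-SD 0.7).
- True count at week t: P − (P − C0) × 0.5^(t/h), with 12% visit-to-visit noise.
- Fast: median h 8 weeks, median P 1.6. Medium: 16 weeks, 1.6. Slow: 30 weeks, 1.4.
- No exits to other therapy.

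**Week 24, two-visit rule, nobody tested after recovery:**

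| Recovery | Still sampled | Mean, sampled | Mean, all | Below LLN, sampled | Below LLN, all |
|---|---|---|---|---|---|
| Fast | 14% | 1.06 | 1.47 | 40% | 8% |
| Medium | 34% | 1.01 | 1.29 | 50% | 20% |
| Slow | 67% | 0.91 | 1.02 | 70% | 51% |

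Consistency check, medium case: the all-subject mean is 0.34 × 1.01 + 0.66 × x = 1.29, so x = (1.29 − 0.343)/0.66 = 1.43. The 66% no longer sampled average 1.43, and the table would omit them.

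Under the single-count rule at Week 24, 5%, 16% and 44% are still sampled, their means are 0.96, 0.92 and 0.84, and 63%, 71% and 83% of them are below LLN.

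**Trend, two-visit rule.** Nobody can leave before the Week 8 visit, so Week 8 is a common origin. Change in mean from Week 8 to Week 50:

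| Recovery | All subjects | Sampled, none tested after recovery | Sampled, 30% tested after recovery |
|---|---|---|---|
| Fast | 1.18 to 1.59 (+0.41) | 1.18 to 1.12 (−0.06) | 1.18 to 1.53 (+0.35) |
| Medium | 0.99 to 1.48 (+0.49) | 0.99 to 1.11 (+0.12) | 0.99 to 1.37 (+0.38) |
| Slow | 0.83 to 1.19 (+0.36) | 0.83 to 1.01 (+0.18) | 0.83 to 1.09 (+0.26) |

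The last column stands for early discontinuers who keep scheduled hematology. It is generous, because it tests them at every time point.

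**Sensitivity to inputs.** With starting counts 0.5 to 0.98, median plateau 1.6, noise 10% and median half-times 8, 16 and 32 weeks, the two-visit rule gives 46%, 51% and 62% below LLN among those sampled at Week 24, against 8%, 17% and 36% of all subjects.

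**Time to recovery.** In the first set of scenarios, 6%, 18% and 50% of subjects are still followed at Week 50 under the two-visit rule. A summary without censoring has no defined way to count those who remain unrecovered.

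**The case against.** Several points on the other side have force.

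- **The shape of the curve.** A reader might infer that the curve must look flat by construction. The documents do not support that. With no testing after recovery, the observed mean falls slightly with fast recovery and rises with medium or slow recovery. With 30% still tested after recovery, it rises in all three cases. What stands is that the rise is damped and the later level too low.
- **Who is in the table.** A reader might also infer that everyone sampled late still has a low count. Under the two-visit rule that is wrong: 60%, 50% and 30% of those sampled at Week 24 are at or above LLN, with recovery not yet confirmed.
- **Time to recovery is already planned.** This is the strongest objection, since that summary is the right tool. It narrows the gap but does not close it, because recovery and censoring are undefined and the SAP footnote and protocol v3.0 notes describe recovery differently.
- **The population is named, n is shown and graphs are optional.** All true, so depletion would be visible. A falling n does not say whether subjects left through recovery, a therapy start or loss, and the bias is in the table with or without a graph.
- **The error is in the cautious direction.** Selection by recovery makes recovery look worse, so it does not hide persistent lymphopenia. Exits to commercial BG00012 or another therapy can remove subjects who are still low, and the direction of that effect is unknown.
- **The inputs are assumed.** They are, so the percentages are illustrative.

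**Conclusion.** The point holds in this form: followed as written, SAP 6.3.2.3 yields later post-treatment statistics biased towards slow recoverers, which understate recovery. The direction follows from the stopping rule. The size does not. In the scenarios without testing after recovery, the Week 24 mean is too low by 0.41, 0.28 and 0.11 multiples of LLN (1.47 − 1.06, 1.29 − 1.01, 1.02 − 0.91). The gap narrows where discontinuers keep scheduled hematology. These figures rest on assumed starting counts, plateaus, half-times and noise, and on no exits to other therapy; they show direction and range only.

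This is a descriptive safety summary. The primary analysis (incidence of AEs, SAEs and discontinuations due to AEs) is unaffected.

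**What to change.** In SAP 6.3.2.3:

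1. Make the main post-treatment summary the cumulative proportion recovered (Kaplan-Meier or cumulative incidence) in a fixed cohort: all subjects with a count below LLN at the last dose. List separately any who first fall below LLN afterwards.
2. Use one recovery definition, and say which visit date counts as recovery. SAP Section 3, Table 2, footnote 3 must first be reconciled with the protocol v3.0 notes to Tables 2 and 4, including the therapy exits.
3. Censor at end of follow-up. Treat the start of commercial BG00012 or another MS therapy as censoring or as a competing event, and state the assumption. Censoring assumes that starting therapy is unrelated to the chance of recovery.
4. At each time point show the numbers still followed, recovered and otherwise exited.
5. If by-time means are kept, label them as counts among subjects still in follow-up, not as a recovery curve. Do not carry recovered counts forward. Under similar assumptions (half-times 8, 16 and 32 weeks), that gave Week 50 means of 1.30, 1.21 and 1.14 against 1.60, 1.50 and 1.33 with complete follow-up, because it freezes the count soon after it crosses LLN.

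The cost is a few lines of SAP text, one reprogrammed table and an explicit assumption about therapy switches. No new data or visits are needed.
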